3.0 STUDY DESIGN

This is an open-label, randomized Phase II trial to determine whether MMF given over 22 months meaningfully decreases the size of the HIV reservoir.

At the University of Washington in Seattle, we will enroll 5 study participants who have been on ≥ 2 years of suppressive ART. Study participants will be followed closely for at least 22 months with safety labs and serial measurements of the HIV reservoir (specifically, cell-associated HIV DNA and mRNA (**ca-DNA & ca-RNA**), quantitative viral outgrowth assay (**QVOA**), and single copy plasma viral

Clinical Protocol

load (**scVL**)). A “go/no-go” decision will occur after 12 months based on pre-defined thresholds of reduction in the HIV reservoir measured with ca-DNA.

All participants will be offered enrollment in a sub-study in which an anoscopy with rectum biopsies is performed on 3 occasions to assess the reservoir in the gastrointestinal lymphatic tissue (**GALT**).

We will vaccinate study participants with the annual influenza vaccine and analyze their humoral response to this vaccine approximately one month later with a routine blood draw done in conjunction with a safety labs blood draw.

We hypothesize that low doses of MMF will be well tolerated among healthy HIV-infected study participants who have fully ART-suppressed HIV. We hypothesize that the incidence of opportunistic infections will not exceed that of comparable larger cohorts of HIV-treated patients. Of note, certain opportunistic infections such as herpes zoster or HSV-2 recurrence continue to occur despite suppressive ART, while pneumocystis pneumonia, CMV end organ disease, cryptococcus and many other opportunistic infections are much less common in this context. Therefore, in the event of an infection, we will confer with the data safety management (DSM) panel to discuss whether this event is directly attributable to MMF. Finally, we hypothesize that peripheral blood CD4+ and CD8+ T cell counts will remain unchanged throughout MMF therapy, and that HIV replication will remain controlled on ART with addition of MMF.

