If a participant develops nausea or diarrhea anytime during the first week on MMF 500 mg daily, we will offer the participant a change from MMF 500 mg daily to Myfortic© 360 mg daily. Myfortic© is an enteric coated version of MMF which is associated with less nausea and diarrhea in certain patients. If the participant tolerates the first week of Myfortic© 360 mg daily, then we will switch to Myfortic© 360 mg twice daily during the second week. If this is tolerated, then we will test for an anti-proliferative effect per protocol.

In the case of refractory nausea or diarrhea after week one, participants will be offered a change from MMF 500 mg twice daily to Myfortic© 360 mg twice daily. If a study participant is on MMF 750 mg twice daily, then we will switch to Myfortic© 540 mg twice daily. Participants will always have the option of withdrawing their participation from the trial rather than switching to Myfortic©.

Follow-up Visits (approximately 30 minutes)

Over the course of the study, we will ask participants to come in 19 more times (**Table 2**). Starting at entry, for the first month, we will ask them to come in weekly, then every other week for two months, then every month for the rest of the first 12 months, then at month 15, month 18½, and a final visit at 22 months. The purpose of these visits is to obtain samples to measure how the drug is affecting the HIV reservoir and to check safety labs.

We will check to see if the amount of HIV infected cells is decreasing after one year and after two years. If not, then we will ask the participant to stop participating in the study as we wish to see an effect of the drug at that point in time.

Influenza vaccination will occur at one follow-up visit unless study participants have already received this vaccine in the community.

During these visits, we will do the following:

Clinical Protocol

- 1) Draw between 6.5 and 255 mL of blood depending on visit (**Table 2**).
- 2) Draw 2 sets of blood separated by an hour to obtain peak and trough drug levels (weeks, 12, 24, 48, 74 & 88).
- 3) Perform follow up urine pregnancy testing in female participants (point-of-care-test in the clinic)
- 4) Ask how the participant is tolerating the study medication
- 5) Answer any questions
- 6) Discuss continuation in the study
- 7) Perform a focused physical exam as needed

Optional Rectal Biopsy Visit (up to 2 hours)

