6.4 Criteria for Treatment and Individual Study Participant Discontinuation

- The subject requires treatment with disallowed medications
- Pregnancy
- Nausea, vomiting or diarrhea refractory to anti-emetic medications
- Drug toxicity that requires permanent study drug discontinuation as defined in Section 6.2.
- If a participant does not plan to continue with the study
- Go / no-go criterion at month 12: participants must have at least a 0.25 log reduction from baseline at 12 months to continue on MMF. If this criterion is not met, participants will continue to be followed off study drug.
- Subject stops their antiretroviral therapy regimen for greater than 2 weeks
- The subject refuses further treatment and/or follow-up evaluations and decides to discontinue participation in the study
- The investigator determines that further participation would be detrimental to the subject's health or well-being
- The subject experiences virologic failure. Virologic failure will be managed according to local guidelines. In this study, virologic failure is defined as plasma HIV RNA \geq 1,000 copies/mL (confirmed by repeating the assay on 2nd aliquot of the same specimen). If a participant has a viral load between 500-1000 HIV RNA copies, then we will call the participants for an immediate recheck of their viral load as soon as possible and will continue to do so, until this value normalizes or meets criteria for virologic failure. Of note, viral load may be checked by the participant's primary care provider outside of the study: these values will be available to the study PI and the criteria for virologic failure will be the same.
- The subject fails to comply with the study requirements so as to cause harm to him/herself or seriously interfere with the validity of the study results

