8.2 Statistical outcomes

8.2.1 Main statistical outcome

- Change in cell-associated HIV DNA (ca-DNA) reservoir size as measured by multiplexed digital droplet PCR in study participants on versus off MMF (historical controls).

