8.6 Analyses

Aim one anticipated results: We hypothesize at least 0.25 log reductions in the HIV reservoir at month 12 in study participants who have a demonstrated anti-proliferative response to MMF treatment. We hypothesize that cell-associated HIV DNA will undergo a shift from predominantly residing in T_{CM} and T_{EM} to predominantly residing in T_N and T_{SCM}. Further, we predict that reservoir depletion will occur with equivalent rates in blood, and GALT.

We will compute the change in reservoir volume in two ways. First, descriptively, we will use individual linear regressions to compute a slope in log viral load (**VL**) for each participant using time as the only covariate; and then we will describe the mean and standard deviation of that slope. Secondly, we will use linear mixed effects models, as others have done,^{60,61} to estimate an average slope using all the data at once, and a random intercept and slope per person. Estimation of a fixed effect for the interaction of time with treatment arm will help us determine whether the reservoir decreases more quickly with ART+MMF than with ART only in historical controls. We will assess the changing composition of the reservoir using similar models and include the proportion of cells that are naive (T_N) as the outcome in a generalized linear mixed model with a log link. An interaction of time by treatment arm will determine whether rate of change in composition differs by arm.

Clinical Protocol

Aim two anticipated results. We hypothesize that low doses of MMF will be well tolerated among healthy HIV-infected study participants who have fully ART-suppressed HIV. We hypothesize that the incidence of opportunistic infections will not exceed that of comparable larger cohorts of HIV-treated patients. Of note, certain opportunistic infections such as herpes zoster or HSV-2 recurrence continue to occur despite suppressive ART, while pneumocystis pneumonia, CMV end organ disease, cryptococcus and many other opportunistic infections are much less common in this context. Therefore, in the event of an infection, we will confer with the DSM panel to discuss whether any event is directly attributable to MMF. Additionally, we hypothesize that peripheral blood CD4+ and CD8+ T cell counts will remain unchanged throughout MMF therapy, and that HIV replication will remain well controlled on ART with the addition of MMF.

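### Time on MMF and the reading time of the primary endpoint depend on ca-DNA response, but Section 8.6 has no rule for time after a no-go, and Sections 6.1 and 6.4 conflict on that point

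*Combined protocol and SAP*

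**What the plan says.** - **Gate and outcome.** Section 3.0 bases the month-12 decision on ca-DNA. Section 6.4 sets the threshold: "participants must have at least a 0.25 log reduction from baseline at 12 months to continue on MMF". Section 8.2.1 makes change in ca-DNA the main outcome, compared "in study participants on versus off MMF (historical controls".
- **Duration.** Section 9.0 expects that the gate may end MMF early in some or all participants, who are not replaced. Section 8.1 allows extension past 22 months where the reservoir is still falling but detectable. The Endpoint row of the Protocol Summary places the primary endpoint when drug treatment ends, without naming a month.
- **Analysis.** Section 8.6 says "we will use individual linear regressions to compute a slope in log viral load" for each participant, with time as the sole covariate. It then plans a mixed model "to estimate an average slope using all the data at once, and a random intercept and slope per person", with a time-by-arm interaction to judge "whether the reservoir decreases more quickly with ART+MMF than with ART only in historical controls". It gives no window and no term for time off drug.
- **After a no-go.** Section 6.4: "If this criterion is not met, participants will continue to be followed off study drug". Section 6.1, whose test is only whether HIV-infected cells are decreasing: "If not, then we will ask the participant to stop participating in the study". Section 3.0 sides with continued follow-up: "Study participants will be followed closely for at least 22 months with safety labs and serial measurements of the HIV reservoir". So does the 22-month follow-up in the Protocol Summary. Section 6.6 gives those who withdraw laboratory and safety visits and does not mention reservoir sampling.

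**The concern.** The variable being analysed also decides how long each participant is treated and, on one reading of the text, how long each is measured. This has three consequences.

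1. The primary endpoint mixes reading times that depend on response.
2. If no-go participants stay in follow-up, Section 8.6 does not stop their off-drug time from being fitted as MMF time, although the question is about ART plus MMF.
3. If they leave, the unweighted mean of individual slopes can be distorted by assay error. Later data correct a month-12 value that is low by chance in those who pass. Nothing corrects a value that is high by chance in those who fail.

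The same five participants could therefore give different answers on the progressive-decrease hypothesis (2.1d), depending on a data rule that may be chosen after the month-12 results are known.

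**Working it through.** **The plan's own figures (Section 8.4.1).** 12 × 0.0068 = 0.0816 log/yr on ART alone; 1 − 10^(−0.0816) = 17.1%; 12 × 0.017 = 0.204. These reproduce the stated 0.082, 17% and SD 0.2. At a true fall of 0.25 log/yr the excess over ART is 0.25 − 0.0816 = 0.1684.

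**Assumptions.** The documents give no SD for ca-DNA, and 0.2 is a QVOA figure. I take 0.2 for the 12-month change, with range 0.1 to 0.3, divided between assay error and true differences between participants. Table 2 is broken, so ca-DNA is assumed at months 0, 3, 6, 12, 15, 18.5 and 22. The log viral load in Section 8.6 is read as ca-DNA.

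**1. Chance of a no-go.** P(pass) = Φ((true fall − 0.25)/SD), and P(at least one no-go of five) = 1 − P(pass)^5. At SD 0.2:
- true 0.25: 1 − 0.5^5 = 0.97 (the same at any SD)
- true 0.40: 1 − 0.773^5 = 0.72 (0.29 to 0.84 over the SD range)
- true 0.60: 1 − 0.960^5 = 0.18 (0.00 to 0.48)
- Section 6.1's literal test, any decrease, true 0.25: P(pass) = Φ(0.25/0.2) = 0.894, giving 1 − 0.894^5 = 0.43

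**2. End-of-drug change, true 0.25, gate 0.25.** The fixed-time values are 0.25 at month 12 and 0.25 × 22/12 = 0.46 at month 22.
- All variation real: 0.25 + (10/12)(0.5 × 0.25 + 0.399 × SD) = 0.387, 0.420, 0.454 for SD 0.1, 0.2, 0.3.
- All assay error: the half who fail average 0.25 − 0.798 × SD and the half who pass average 0.458 + 0.399 × SD. The overall mean is 0.334, 0.314, 0.294.

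The range is 0.29 to 0.45.

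**3. No-go participants followed, off-drug time pooled as MMF time.** Suppose the drug effect ends with the drug. On the assumed visits, a change of slope at month 12 enters a straight-line fit with weight 172.1/404.2 = 0.426.
- Every no-go participant loses the same excess: 0.25 − 0.5 × 0.426 × 0.1684 = 0.214. The loss is 0.036/0.1684 = 21%.
- All variation lies in drug response, and slopes return to the ART rate: 0.25 − 0.426 × (0.5 × 0.1684 − 0.399 × SD). This is 0.248 at SD 0.2 (1% lost) and 0.265 at SD 0.3, an overstatement.
- Half the variation is assay error, SD 0.2 (simulated): 0.231 (11% lost).
- If half the effect persists after stopping, 0.214 becomes 0.232. If all persists, nothing is lost.

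**4. No-go participants leave, mean of individual slopes, true 0.25, SD 0.2, all assay error.** Given the gate result, the baseline and month-12 errors each average 0.5 × 0.798 × 0.2 = 0.0798 in size, with opposite signs.
- Fail (months 0-12, sum of squares 78.75): 0.25 − 12 × 12 × 0.0798/78.75 = 0.104.
- Pass (all visits, sum of squares 404.2): 0.25 + 12 × 12 × 0.0798/404.2 = 0.278.
- Mean 0.191; loss 0.059/0.1684 = 35%.
- Denser visits (months 0, 1, 2, 3, 6, 9, 12, 15, 18.5, 22; sums of squares 119.4 and 543.0): shifts of 0.096 and 0.021, mean 0.2125, loss 22%.
- Section 6.1's literal test, sparse visits: at most about 16%.
- No assay error: no loss.

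The months 0-12 slope in all participants stays at 0.250 throughout. The mixed model gives 0.250 with variances known, and 0.232 to 0.250 when fitted by REML at n=5 and SD 0.2.

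**5. Noise.** The n=5 sampling SD of the pooled slope is 0.046 to 0.103 log/yr at SD 0.2. The slope shifts above are at most 0.059.

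**The case against.** The case against giving this much weight is substantial.

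- The between-arm comparison is the mixed model, which tolerates dropout that depends on ca-DNA values already in the model. The summary with the larger distortion is labelled descriptive in Section 8.6.
- The plan asks about on versus off MMF, and Section 8.1 treats passing the gate as a condition for remaining in the MMF arm. Counting off-drug time as MMF time is possible but is not what that wording suggests. It would also not be a bias for a treatment-policy slope.
- A true fall of 0.25 equals the gate and is close to the worst case. The SD is borrowed from another assay, and Section 8.4.1 says that power is not a prerequisite.

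All of this stands, and it limits the size of the point. It does not supply the missing data rule, fix the endpoint's reading time or remove the conflict between Sections 6.1 and 6.4.

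A reader might infer three stronger things, none of which the documents support.

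- *The planned slope is biased by 21% or 35%, and always downward.* The 21% is an upper bound that needs every no-go participant to lose the same excess, and the direction can reverse (0.265). The 35% needs pure assay error and sparse visits.
- *Failing the 0.25 threshold means leaving the study.* The threshold belongs to Section 6.4, which keeps participants in follow-up. Leaving belongs to Section 6.1, which tests only for a decrease. The leaving scenario at the 0.25 gate is one possible resolution of the conflict.
- *An inert drug would appear effective.* That would need a month-22 summary restricted to those who pass, and no section proposes one.

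**Conclusion.** The point holds as a design and analysis gap. Treatment duration and the primary endpoint's reading time depend on the main outcome, and Section 8.6 does not say how time after a no-go enters. At a true 0.25 log/yr the gate would almost certainly bring this into play (0.97 at the 0.25 threshold, 0.43 under the literal decrease test at SD 0.2).

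The clearest effect is on the endpoint. Its expected value of 0.29 to 0.45 log corresponds to no common time point. For the slopes at SD 0.2, pooling off-drug time loses 1 to 21% of the excess over ART. If no-go participants leave at the 0.25 gate, the descriptive mean loses 0 to 35%, while the mixed model stays approximately unbiased. With five participants these slope shifts are modest against sampling noise. Their size and direction depend on assay error, where the heterogeneity lies, persistence of the effect and the visit schedule, none of which the documents settle. The change should be made, but this does not invalidate the trial.

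**What to change.** In Section 8.6:

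1. Report the month-12 ca-DNA change in all Step 3 participants as the common-time reading of the primary endpoint. Label any month-22 or extension result on drug as conditional on passing the gate.
2. Compute the descriptive individual slopes over months 0-12 for every Step 3 participant, and show later data separately by on-drug or off-drug status.
3. If no-go participants are followed, give time since MMF stopped its own slope in the mixed model, separate from on-MMF time and from the historical controls. Compare the on-MMF slope with the historical ART-only slope.
4. Reconcile Sections 6.1, 6.4, 6.6 and 3.0 and the Protocol Summary on the month-12 criterion and on whether no-go participants stay in follow-up with ca-DNA sampling. State how extension data under Section 8.1 enter the endpoint. No clinical rule is proposed here.

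The cost is SAP wording and one model term, with some loss of precision. At n=5, SD 0.2 and a true 0.25, the sampling SD is 0.084 to 0.090 for the months 0-12 slopes and 0.057 to 0.082 for the on-MMF slope, against 0.051 to 0.093 for the pooled slope. The off-drug slope will be imprecise. If all five pass (3% at a true 0.25, 28% at 0.40, 82% at 0.60, with SD 0.2), the model reduces to the planned one. The rule should be fixed before any month-12 data are seen.

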9.0 HUMAN SUBJECTS

Participant will be 5 adults and children ≥ 18 and ≤ 65 years of age. Participants will have received ART for at least 2 years with demonstration of full viral suppression during this time, documented by at least four negative plasma viral loads and no more than one plasma viral blip during this time. They will also have a current CD4+ T cell count of $\geq 350/\mu\text{l}$. The participants will receive 500mg MMF twice daily in addition to their ART regimen. The planned MMF treatment duration is 22 months, but efficacy Go/no-Go algorithms at the end of month 12 may lead to earlier termination of MMF treatment in some or all study participants.

All study participants must plan to reside in the Seattle area for the duration of the study. We anticipate pre-screening 30 potential study participants by medical charts to identify 15 who will be approached by study staff to schedule an in-person eligibility visit; the first 5 available study candidates will enter the anti-proliferation test phase receiving MMF for one week. We conservatively estimate that 1 of these 5 individuals will fail to document adequate T cell anti-proliferation and not be enrolled in this study. We will continue to screen and test until we enroll 5 participants with a verified in vivo anti-proliferative effect of MMF, who will then continue to take MMF for 22 months. Participants who discontinue MMF treatment due to inadequate efficacy in reducing the latent HIV reservoir at the 12 month Go/no-Go decision point, or due to treatment related side effects, will not be replaced.

Potential Risks include:

(1) Stress and anxiety could result from study participation. These will be minimized by careful explanation of study procedures, and maintenance of an open, supportive attitude by study personnel.

(2) Potential risks from participation in this study include those related to blood draws. All personnel responsible for blood drawing will be experienced phlebotomists who will follow standard procedures. Blood draws can be uncomfortable and cause bruising. Some temporary anemia could occur from study phlebotomy. A record of all study phlebotomies and blood volume drawn will be maintained for each participant, and total blood collection for clinical care and the study will be monitored and IRB limits for study purposes will not be exceeded. Specifically, individual blood draws will never be more than 270 mL and total volumes of blood drawn over an eight-week period will never be more than 450 mL.

(3) Insertion of an anoscope may be uncomfortable. Rectal biopsies usually do not hurt. However, it is possible subjects could feel some brief pain or discomfort. In rare cases, these biopsies may

Clinical Protocol

cause a significant amount of bleeding or, rarely, an infection at the site that was sampled. In extremely rare circumstances, rectal biopsies can result in rectal perforation. Lidocaine cream may cause local numbness, redness, swelling or irritation. Extremely rare side effects include irregular heartbeat, shortness of breath and seizure. Precautions will be taken by the experienced study gastroenterologist at the time the biopsies are obtained to prevent perforation and to prevent or minimize bleeding and infection. In addition, as a further precaution, participants will be asked not to have anal sex for 5 days after the biopsies to help prevent any possible increase in risk of infection or bleeding.

(4) Answering questions about smoking, alcohol use, and sexual behaviors may make subjects feel uncomfortable.

(5) There are also potential risks related to confidentiality. All participating staff and faculty at the site will maintain the confidentiality of study subjects, and study materials that could expose identity will be kept in locked cabinets or in password-protected files, accessible only to the study personnel at the research clinic conducting the study with a need to know.

(6) Reports of MMF adverse reactions are based on dosages of 2-3 grams daily (rather than 1g daily in this study). A detailed description of all adverse effects and precautions is contained in the CellCept® Product Monograph, which is included in the Appendix to the Clinical Protocol. (Of note, we will be using the generic version of MMF and not CellCept.)

The principal adverse reactions associated with the oral administration of MMF include diarrhea, leukopenia, sepsis, and nausea and vomiting. There also is evidence of a higher frequency of certain types of infections, e.g., cytomegalovirus viremia, JC virus-associated progressive multifocal leukoencephalopathy (PML) and polyomavirus-associated nephropathy (PVAN). Patients receiving MMF alone or as part of an immunosuppressive regimen are at increased risk of developing lymphomas and other malignancies, particularly of the skin. These risks appear to be related to the intensity and duration of immunosuppression rather than to the use of any specific agent.

There are also a small number of patients who received solid organ transplants and experienced reversible falls in their red cell or white cell counts while receiving MMF. Additionally, cases of Pure Red Cell Aplasia (PRCA) have been reported in some patients receiving MMF. PRCA is a condition in which the bone marrow stops producing red blood cells. In some instances, PRCA can be reversed by reducing or stopping MMF.

MMF has embryo-fetal toxicity, causing fetal harm when administered to a pregnant female. Use of MMF during pregnancy is associated with an increased risk of first trimester pregnancy loss and an increased risk of congenital malformations, especially external ear and other facial abnormalities including cleft lip and palate, and anomalies of the distal limbs, heart, esophagus, kidney and nervous system.

There will be adequate protection against risks including IRB approval at the study site, written informed consent, rapid reporting of adverse events and data safety monitoring as above.

(8) Use of ondansetron is occasionally associated with diarrhea, headache, fever, lightheadedness, dizziness, weakness, fatigue, constipation, rash, blurred vision, urinary retention, and muscle spasm.

(9) The most common adverse reactions ($\geq 20\%$) for Myfortic® include anemia, leukopenia, constipation, nausea, diarrhea, vomiting, dyspepsia, urinary tract infection, CMV infection,

Clinical Protocol

insomnia. Rare more severe complications include pure red cell aplasia and Progressive multifocal leukoencephalopathy (PML).

